3. SUMMARY OF STUDY DESIGN

[figure not shown]
This Phase 4, double-blind, randomized, placebo-control, multicenter study will evaluate the effect of OCA on clinical outcomes in subjects with PBC who are at higher risk of liver-related clinical complications.

Eligible subjects will have a diagnosis of PBC with bilirubin levels $>ULN$ and $\leq 5x ULN$ and/ or $ALP > 3x ULN$. Subjects will be screened twice during a 1- to 8-week Screening period prior to entering the study to allow for the collection of repeat serum chemistry samples (at least 2 weeks apart) to confirm pretreatment alkaline phosphatase (ALP) and total bilirubin values.

Investigational product (IP) will be taken orally, once daily for the majority of subjects; dose and frequency will be modified for subjects with cirrhosis (including subjects progressing to cirrhosis during the study) and classified as Child-Pugh B or C. The randomization will be stratified by ursodeoxycholic acid (UDCA) treatment (yes/ no) and baseline bilirubin categories ($>$ upper limit of normal [ULN]/ $\leq ULN$). A minimum of 30% of subjects will have elevated bilirubin ($>ULN$) at Screening.

The study is event driven and will continue until approximately 127 adjudicated primary endpoint events have been accrued in unique subjects, or until the Sponsor (eg, based on a recommendation from the Data Monitoring Committee (DMC)) terminates the study. Subjects are expected to be followed for a minimum of approximately 6 years. Figure 1 below displays the study design diagram. Schedules of study procedures are outlined in Table 1 (Screening to Month 12) and Table 2 (Year 2 to End-of-Study Endpoints) of the study protocol, where more details are provided.

Figure 1: Schematic Diagram Study 747-302

EOS = end of study; M = month, OCA = obeticholic acid; ULN = upper limit of normal
 Initial dose titration of investigational product should occur at the Month 3 visit, or any study visit thereafter for subjects on all dosing regimens, based on tolerability and biochemical response (Up-titration should be considered when ALP and/ or total bilirubin are $>ULN$). Subsequent dose titration(s) for subjects classified as Child Pugh B or Child-Pugh C and following a modified dosing schedule may occur no earlier than 6 weeks after the previous dose titration.

Dosing frequency will be determined by the presence or absence of cirrhosis and, if cirrhosis is present, by Child-Pugh Score as described below:

	Planned Dosing Regimen	

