8.3.3. Prognostic Endpoints and Markers of Inflammation

Change and percentage change from Baseline for MELD score, MELD-Na score, Child-Pugh score, Mayo Risk Score (MRS), IgM, C-reactive protein (CRP), tumor necrosis factor- α (TNF- α), FGF-19, cytokeratin-18 (CK-18), C4, and enhanced liver fibrosis (ELF) score will be summarized and analyzed using the Wilcoxon Rank Sum Test to compare groups at annual timepoints. The median differences and 95% CI of the median differences between treatment groups will be constructed using Hodges-Lehmann estimate. If the median differences between treatments are not approximately symmetrical around the median, the Sign Test may be used.

Values below or above the quantifiable limits will be handled as follows. Quantitative laboratory tests containing less than (<) and greater than (>) symbols are test results that are below and above quantifiable limits, respectively. In order to retain these values for analysis purpose, the following imputations will be done within the analysis datasets:

For laboratory test results that are below the quantifiable limit:

$$\text{Imputed laboratory results} = (\text{numeric portion of the result}) \times 0.9.$$

For laboratory test results that are above the quantifiable limit:

$$\text{Imputed laboratory results} = (\text{numeric portion of the result}) \times 1.1$$

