All statistical tests comparing groups will be conducted at the 2-sided, 0.05 level of significance, unless otherwise specified (eg, the primary efficacy analysis, [Section 8.6](#)). Summary statistics for each treatment group will be presented, as well as 95% CIs comparing groups.

Baseline Definitions

The Baseline value for statistical analyses of quantitative parameters is defined as the mean of all available study evaluations after the subject signs the informed consent and prior to or on the first administration of investigational product, unless otherwise specified. If there is only one evaluation prior to the first administration of investigational product then the available data from this evaluation will be used as the Baseline value.

The baseline value for analyses of lipid parameters is defined as the last fasted evaluation prior to the first administration of IP.

The baseline value for analyses of qualitative parameters (eg, normal/abnormal) is defined as the last evaluation prior to the first administration of IP.

Baseline values defined above will not change regardless if a subject stops taking investigational product and begins taking commercially marketed OCA.

Visit Windows

Visit windows, as provided below, will be established relative to an individual’s Day 0, the date of first administration of investigational product. Analyses will use visit windows defined by relative day, overriding CRF designated visit numbers.

OCA Therapy 3-Month Interval Visit Windows (Days)

Months	Target Study Day ^a	Analysis Window Study Day ^a	
		Low	High
Day 0	1	Closest visit to Day 1, prior to first IP dose ^b	
Month 1	30	2	46
Month 3	90	47	137
Month 6	183	137	227
Month 9	274	228	318
Month 12	365	319	410
...
Month n^b	$\text{round}(365.25/12*n)$	$\text{round}(365.25/12*n) - 46$	$\text{round}(365.25/12*(n+3)) - 47$

Note: Follow-up visits are not included in visits windows.

^a Study day will be calculated from first dose date.

^b For n in three month increments (15, 18, 21, ...).

Partial Dates

If only a partial date is available and is required for calculation, the following standards will be applied:

- Diagnostic Date (eg, PBC diagnostic date)
 - For missing day only – Day will be imputed as the first day of the month (ie, 1).
 - For missing day and month – Day and month will be imputed as the first day of the year (ie, 1 January).
- Start Dates (eg, event date, AE onset date, or start date of medication)

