5. SUBJECTS

The study aimed to enroll approximately 428 subjects. At study end, approximately 334 subjects were enrolled, and approximately 40 consented to the serial PK substudy.

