12.1. Key Subgroups for Evaluation

To fulfill the scope of the analysis, the following subgroups have been identified for the evaluation based on known association of risk with clinical outcomes PBC or end-stage liver disease. Further PK assessment by these groups may be required, based on outcomes.

Subgroups Defined by Baseline Disease Severity:

- Cirrhotic vs Noncirrhotic
 - Cirrhosis as defined by baseline status on the cirrhosis case report form and screening/baseline CP Evaluation
- Noncirrhotic vs Child Pugh A vs Child Pugh B
 - Subjects who received daily dosing vs those who received the modified dosing regimen
- Noncirrhotic vs Child Pugh A5 vs Child Pugh A6 vs Child Pugh B7 vs Child Pugh B8 vs Child Pugh B9
- Baseline/Medical History of clinically significant portal hypertension (CSPH) vs Patients with No Baseline/Medical History of CSPH defined by any of the following:
 - Previous history of portal hypertension includes procedures for transjugular intrahepatic portosystemic shunt (TIPS), sclerotherapy, ligation, hepatic venous pressure gradient (HVPG) measurement >10 mmHG, paracentesis, thoracentesis (due to hepatic hydrothorax)
 - Baseline biochemical evidence of portal hypertension
 - Previous history or baseline observation of the terms defined in Table 4.

Table 4: Adverse Event Terms Associated Used to Define Presence or Absence of Clinically Significant Portal Hypertension (CSPH)

Presence of CSPH based on SMQ terms	Severity
Presence of collateral circles secondary to CSPH (SMQ Terms: Varices - Anorectal, Duodenal, Esophageal, Gastric, Intestinal, Splenic, Gallbladder, Peripancreatic – Portal Hypertensive Gastropathy and Enteropathy)	Any
GI Bleeding (SMQ Terms Gastric Variceal Hemorrhage, Oesophageal Variceal Hemorrhage, Anorectal variceal hemorrhage)	Any
Ascites (SMQ terms Ascites, Hepatic Hydrothorax, Oedema due to hepatic disease, Peritonitis Bacterial, bacterascites)	Any
Multiorgan complication: Hepatopulmonary syndrome, hepatorenal syndrome.	Any
Portopulmonary Hypertension	Any

- Baseline MELD \geq the following thresholds:
 - 8
 - 11
- Baseline Rotterdam Classification (mild vs moderate vs severe)
- Baseline GLOBE Score \geq the following thresholds:
 - Age Specific Thresholds
 - -0.52 for <45 years; 0.01 for \geq 45 to <52 years; 0.60 for \geq 52 to <58 years; 1.01 for \geq 58 to <66 years; 1.69 for \geq 66 years
 - 0.9
- Baseline Mayo Risk Score \geq the following thresholds:
 - 7.43
 - 8.50
 - 9.10

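### If most Child-Pugh scores do not change, the planned Hodges-Lehmann estimate and 95% CI can be exactly 0 (0 to 0) beside a significant Wilcoxon test

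*SAP*

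**What the plan says.** Section 8.3.3 puts Child-Pugh score in one list with MELD, MELD-Na, Mayo Risk Score, IgM, CRP, TNF-α, FGF-19, CK-18, C4 and ELF. Change and percentage change in all 11 "will be summarized and analyzed using the Wilcoxon Rank Sum Test to compare groups at annual timepoints". The between-arm estimate is the same for all: "The median differences and 95% CI of the median differences between treatment groups will be constructed using Hodges-Lehmann estimate". The only fallback is optional and concerns asymmetry: "If the median differences between treatments are not approximately symmetrical around the median, the Sign Test may be used". No rule covers ties or discrete scores.

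The clinical pharmacology analysis plan, bound in the same file, shows that the score moves in whole points (its section 12.1): "Noncirrhotic vs Child Pugh A5 vs Child Pugh A6 vs Child Pugh B7 vs Child Pugh B8 vs Child Pugh B9". SAP Appendix A sets the baseline of a quantitative parameter as "defined as the mean of all available study evaluations after the subject signs the informed consent", up to first dose, so half-point changes are possible. Under section 8.6, secondary endpoints outside the key list are tested at a nominal two-sided 0.041.

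**The concern.** A Hodges-Lehmann shift suits continuous markers. For an integer score that often stays the same, many pairwise differences are exactly 0. If those zeros cover the middle of the distribution of differences, the estimate and both limits are 0. The table would then show a zero-width interval at no effect next to a test that rejects no effect. The interval would look perfectly precise and say nothing about how many more subjects worsened in one arm. Percentage change has the same mass at 0 and the same problem.

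At stake is whether the one between-arm estimate planned for the score change can be interpreted. The score matters in this trial, because new onset of Child-Pugh ≥7 is a Group 2 component of the primary endpoint.

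**Working it through.** The SAP gives no figure for this analysis, so there is none to reproduce.

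**Inputs from the documents.** 1:1 allocation (SAP 3.1); test level 0.041 (SAP 8.6); and, from section 5 of the clinical pharmacology plan, "At study end, approximately 334 subjects were enrolled", so at most about 167 per arm.

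**Assumed inputs.** The numbers with a value at an annual visit and the distribution of change. Higher scores are worse, so a negative OCA-minus-placebo difference favours OCA.

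**Formulas** for m and n subjects:
- Estimate: median of the mn pairwise differences.
- Lower limit: the k-th smallest difference, k = mn/2 − 1.96·√(mn(m+n+1)/12). The upper limit is its mirror image.
- Both limits are therefore 0 when the shares of negative and of positive differences are each below k/mn.

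At 150 per arm, k = 11,250 − 1.96·√(22,500·301/12) = 9,778, so k/mn = 43.5%. The threshold is 43.8% at 167 per arm, 42.0% at 100, 39.6% at 60 and 35.3% at 30.

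**Two worked examples**, 150 per arm, counts for changes of −1, 0, 1, 2, 3:

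| | Example 1 | Example 2 |
|---|---|---|
| Placebo counts | 6, 99, 26, 13, 6 | 8, 82, 33, 18, 9 |
| OCA counts | 6, 123, 14, 6, 1 | 8, 112, 18, 9, 3 |
| Unchanged, OCA v placebo | 82% v 66% | 75% v 55% |
| Worse by ≥1 point, OCA v placebo | 14% v 30% | 20% v 40% |
| Negative / zero / positive pairs | 6,701 / 12,661 / 3,138 | 8,423 / 10,031 / 4,046 |
| Negative and positive shares | 29.8%, 13.9% | 37.4%, 18.0% |
| Hodges-Lehmann (95% CI) | 0 (0 to 0) | 0 (0 to 0) |
| Wilcoxon p, tie-corrected | 0.002 | 0.0006 |
| Mean change, OCA v placebo | 0.15 v 0.43 | 0.25 v 0.59 |
| Mann-Whitney probability (95% CI) | 0.58 (0.53 to 0.63) | 0.60 (0.54 to 0.65) |

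The Mann-Whitney probability is (negative + half of zero)/mn, for example (6,701 + 6,330.5)/22,500 = 0.58. The risk difference in Example 1 is 14% − 30% = −16 points. Its standard error is √(0.14·0.86/150 + 0.30·0.70/150) = 0.047, so the 95% CI is −25 to −7 points.

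**How far it extends.**
- Collapse is certain at 167 per arm once 75% are unchanged in both arms, because at most 1 − 0.75² = 43.75% of pairs can differ.
- In simulated trials with 80% (OCA) v 60% (placebo) unchanged, 0 (0 to 0) occurred together with p<0.041 in 96% at 167 per arm, 81% at 100 and 49% at 60. With 85% v 70% unchanged the shares were 98%, 88% and 56%.
- At an assumed 70% v 55% unchanged in whole points, 44.0% of pairs are negative, just above 43.8%. The estimate is still 0, but the interval is −1 to 0. In simulation it was 0 to 0 in 47% of trials at 167 per arm.
- At 60% v 52% unchanged with movement in opposite directions, the estimate is −1.
- Half-point baselines matter. At 82% v 66% unchanged and 150 per arm, the share of significant trials with 0 to 0 fell from 100% with no half-points to 82–84% when 20% of subjects have them and 5–7% when 40% do.

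**The case against.** The strongest objection is that the premise is assumed. No section gives the share of subjects whose score stays the same. Section 3 says investigational product "will be taken orally, once daily for the majority of subjects", but a dosing majority does not establish stability of the score over years in a population chosen for higher risk. This stands: the problem is conditional. The averaged baseline may also remove many ties, although not if each subject has a single pre-dose score. That stands too.

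A reader might infer that the interval collapses whenever more than half of subjects are unchanged. It does not, as the 70% v 55% case shows.

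A reader might also infer that a real benefit or harm on Child-Pugh would be reported as nil. The SAP does not support that. Appendix A requires means, SDs and quartiles by arm; in both examples the means differ and the upper quartile is 0 on OCA and 1 on placebo. Section 8.3.1 analyses time to each relevant primary component, which includes new-onset Child-Pugh ≥7 in subjects without baseline decompensation, with Gray's test and a Fine-Gray hazard ratio and CI. The Wilcoxon p-value would be shown as well.

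Finally, Hodges-Lehmann is the usual companion of the rank-sum test, and 0 is a correct median when the middle pairwise differences are ties. That is true of the point estimate. It does not make a zero-width interval beside a rejecting test useful to a reader.

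**Conclusion.** The concern holds as a conditional and minor one. If a clear majority of subjects have exactly zero change (roughly 70% or more, depending on arm size and on how one-sided the changes are) and few have half-point baselines, the rule in section 8.3.3 can return 0 (0 to 0) beside p<0.041. For the score change, no other between-arm estimate with a CI is planned; the optional Sign Test supplies none, and the shift tables in section 8.4.1 are for CLIF-C ADs only. The planned interval would then be uninformative and falsely precise.

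The share unchanged and the share with half-point baselines are assumptions that the documents neither confirm nor exclude. The endpoint is an additional secondary outside the key hierarchy, and other planned outputs would show part of the difference. No main conclusion of the trial depends on it.

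**What to change.** Add one sentence to section 8.3.3. For Child-Pugh score, keep the Wilcoxon test, and report as the between-arm estimate the Mann-Whitney probability, P(OCA better) plus half P(tie), with its 95% CI. Add the percentage worsening by at least 1 point in each arm, with a risk difference and CI. Keep Hodges-Lehmann for the continuous markers. Section 8.7 repeats these analyses in subgroups, so the sentence should apply there too.

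The cost is that sentence and a few lines of code, with no new data. The downside is a different effect measure for one of the 11 markers.

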3.1. Randomization and Blinding

This study will be conducted in a double-blind, placebo-controlled manner. Allocation to one of two treatment groups (OCA or placebo) will occur on a 1:1 ratio across sites and will be stratified by UDCA treatment (yes/no) and mean baseline bilirubin categories (>ULN/≤ULN), as specified by the central laboratory. The randomization will be based on a predefined randomization code (generated by the Sponsor or designee) using an interactive web response system (IWRS). The IWRS will also serve as an investigational product inventory and management system and may be integrated with the study database.

The unblinded data access during DMC and interim analysis is described in Safety Review Committee Charter.

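### SAP section 8.3.3 allows the Sign Test as a fallback for comparing two independent arms, where it has no defined form, on a symmetry condition the rank-sum test does not need

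*SAP*

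**What the plan says.** SAP section 8.3.3 covers change and percentage change from Baseline in 11 measures: MELD, MELD-Na, Child-Pugh, Mayo Risk Score, IgM, CRP, TNF-alpha, FGF-19, CK-18, C4 and ELF. Three sentences set the analysis.

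- Test: the measures "will be summarized and analyzed using the Wilcoxon Rank Sum Test to compare groups at annual timepoints".
- Estimate: "The median differences and 95% CI of the median differences between treatment groups will be constructed using Hodges-Lehmann estimate".
- Fallback: "If the median differences between treatments are not approximately symmetrical around the median, the Sign Test may be used".

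On design, SAP section 3.1 states: "Allocation to one of two treatment groups (OCA or placebo) will occur on a 1:1 ratio across sites". Randomization is stratified by UDCA use and bilirubin category. No OCA subject is matched to a placebo subject, and section 8.3.3 creates no such matching. It also gives no criterion for judging approximate symmetry.

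**The concern.** The fallback and its trigger both belong to a different data structure. The Sign Test counts positive and negative signs among paired differences, or among one sample's deviations from a fixed value. Symmetry of those differences is the condition for the Wilcoxon signed-rank test, and the Sign Test is the usual retreat when it fails. The sentence reads like a rule for paired data attached to a two-sample comparison.

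An analyst who followed it would have to invent a pairing, and the p-value would depend on that choice. The permissive wording, with no criterion for symmetry, also leaves the choice of test open until the data have been seen. Each measure is analysed both as change and as percentage change, so the option covers 11 × 2 = 22 comparisons at every annual timepoint. Section 8.7 carries the same endpoints into the baseline disease-stage subgroups.

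**Working it through.** Section 8.3.3 gives no sample size, power or numerical criterion, so there is no figure of the plan to reproduce. The check is a reading of the text plus an illustrative simulation.

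**Inputs**
- Two independent arms, allocated 1:1 (SAP section 3.1).
- Size: the Clinical Pharmacology Analysis Plan bound with the SAP says in section 5: "At study end, approximately 334 subjects were enrolled". This gives 334 / 2 = 167 per arm. Fewer would have data at later annual visits, so 167 is a generous size.
- Assumptions, not in the documents: lognormal data with log-SD 1, a log-shift of 0 or 0.3, two-sided 0.05, and 4,000 replicates.

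**Step 1. Does skewness invalidate the rank-sum test?** Under the null it needs only identical distributions in the two arms. With strongly skewed but identical arms it rejected in 5.4% of replicates (0.05425). The Monte Carlo standard error at 5% is √(0.05 × 0.95 / 4,000) = 0.0034, so the excess is 0.00425 / 0.0034, about 1.2 standard errors. That is consistent with the nominal level, and the test needs no rescue from asymmetry.

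**Step 2. Can a sign test be run on these arms?** Only after pairing subjects arbitrarily. In one simulated dataset with a log-shift of 0.3, the rank-sum p-value was 0.002. The same data were then re-paired at random 2,000 times and an exact sign test run on each pairing:

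| Sign-test result over re-pairings | Value |
|---|---|
| Smallest p | 2e-7 |
| Median p | 0.013 |
| Largest p | 0.64 |
| Share below 0.05 | 81% |

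The data never changed. Only the pairing did.

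**Step 3. What would it cost in power?** With a log-shift of 0.3, power was 77% for the rank-sum test and 57% for the arbitrarily paired sign test. The second figure can be checked by hand. For a random pair, the probability that the shifted arm is higher is Φ(0.3 / √2) = 0.584. With 167 pairs the expected count is 167 × 0.584 = 97.5, with SD √(167 × 0.584 × 0.416) = 6.4. Two-sided rejection at 0.05 needs a count of at least 97. Power is then about Φ((97.5 − 96.5) / 6.4) = Φ(0.16) = 0.56, in line with the simulation.

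**Step 4. Does any other reading make the sentence work?**
- Between-arm median difference, taken literally: this is one number per measure and visit, and one number has no symmetry around its median.
- All cross-arm pairwise differences (167 × 167 = 27,889): counting their signs gives the Mann-Whitney statistic, which is the rank-sum test already named. A binomial sign test on them would be invalid because each subject enters 167 differences.
- Within-arm change from Baseline: a sign test could be run, but it would test change against zero in one arm. The section says it compares groups.

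**The case against.** The case for leaving it alone is about reach, and most of it stands. The sentence says the Sign Test may be used, not that it will be. The rank-sum test with its estimate and interval remains the specified analysis. These are additional secondary endpoints under section 8.3. They lie outside the hierarchical key secondary testing and are tested at a nominal 0.041 level under section 8.6. Section 1 requires departures from the planned methods to be documented in the study report.

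The trigger can also be defended in part. It follows directly on the Hodges-Lehmann sentence, and that estimate is the median of the cross-arm differences. It equals the difference of the two medians under a pure shift, or when both arms are symmetric. Shape therefore bears on how the estimate is described. That stands, but it concerns interpretation of the estimate and gives no reason to change the test, least of all to a paired one.

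Three stronger readings are tempting, and the documents do not support them.
- A reader might infer that the trigger would probably be met because markers such as CRP or IgM are skewed. The trigger is asymmetry of the differences between treatments. Under a pure shift, cross-arm differences are symmetric about that shift however skewed each arm is. In simulated identical lognormal arms, their 5th and 95th percentiles were −3.99 and 4.01. The analysed variables are also changes, and the SAP gives no distributional data.
- A reader might infer that the fallback would end up testing within-arm change from zero. The text says between treatments, so this would be guesswork about an analyst's response.
- A reader might infer that the comparison must become a stratified (van Elteren) test. Whether to stratify is a separate question and does not follow from this error.

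**Conclusion.** The sentence is wrong as written, and nothing elsewhere in the SAP corrects it. The Sign Test has no defined form for two independent arms without a pairing, and the plan gives none. The symmetry condition is not an assumption of the rank-sum test.

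The methodological conclusion rests on the design and the definitions of the tests, not on the simulation. The simulated figures (p from 2e-7 to 0.64 over re-pairings; power 57% against 77%) depend on the assumed lognormal shape, shift and 167 per arm. They illustrate the mechanism and do not predict results in this trial. How often the trigger would be met cannot be determined from the documents.

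The practical size is limited to an optional fallback for 11 nominally tested measures and their disease-stage subgroups. No primary, key secondary or safety conclusion depends on it. It is still worth correcting, because it leaves open a discretionary, data-dependent switch to an inapplicable test.

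**What to change.** Delete the Sign Test sentence from section 8.3.3. Keep the Wilcoxon rank-sum test and the Hodges-Lehmann estimate with its 95% CI for all 11 measures at every annual timepoint, with no switch of test based on the observed data. If useful, add a short note that the Hodges-Lehmann value is the median of cross-arm differences and reads as a shift only when the two distributions have similar shape. If the sponsor wants a second test, it should be a named two-sample method, such as a two-sample median test, reported alongside the rank-sum result and not chosen after inspection.

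The cost is one deleted sentence. No data collection, sample size or other section changes.
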